### Data Analytic Strategy:

**Overview.** Analyses will primarily rely on generalized linear modeling (GLM) for cross-sectional analyses and generalized linear mixed modeling (GLMM) for longitudinal analyses. This approach allows for various outcome distributions and multilevel data. All models will account for repeated observations with via the best-fitting structure of level-2 intercepts/slopes. We will aim to collect full data on 12 participants. Other participants who drop out or are withdrawn will be excluded from analyses, depending on how much data we are able to collect. If only a few data points are missing, generalized linear mixed modeling will natively handle missing outcome data. GLMM natively handles missing data by allowing unequally spaced observations between participants; any other issues related to missing data will be handled via explicit modeling of missingness or imputation. Analyses will be performed in R^72 via packages lme4, rstan, and brms. **Confounders:** Preliminary data analyses will inspect relationships between sample characteristics, predictors, and outcomes via GLMM. Variables that demonstrate a relationship with both the predictor and outcome in a model meet criteria for being potential confounders and yield models with and without covariate adjustment. We report the simpler model if inferences are not affected by these covariates and report both models otherwise.

**Inference:** Analyses will be run in parallel frequentist and Bayesian models. Frequentist results yield the probability of the data (or data more extreme), given the null hypothesis, while Bayesian results directly yield the probability of an alternative hypothesis. Weakly informative priors will be used for all Bayesian analyses in order to emphasize the influence of the present data. **Multiplicity:** All *a priori* frequentist models will be evaluated at the  $\alpha=0.05$  (two-tailed) significance level, and will employ false discovery rate (FDR) to control for Type I error across any *post hoc* analyses. Bayesian models will be evaluated via PP threshold guidelines in the literature suggesting that PP = 75% to 90% indicates moderate evidence, PP = 91% to 96% indicates strong evidence, and PP = 97% or above indicates very strong to extreme evidence. **Assumptions:** Posterior predictive checking, scale reduction factors ("rhat"), and effective sample size will be used to evaluate Bayesian assumptions. Evaluation for frequentist models will use graphical evidence and statistical tests.

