### Primary Hypotheses and Specific Aims:

Primary Aim 1: Determine the effects of SUVO on sleep, stress, and cue reactivity/craving

Hypothesis 1a: SUVO compared to placebo will improve sleep outcomes assessed by actigraphy (total sleep time, wake after sleep onset), self-report (Pittsburg Sleep Quality Index), and EEG (resting state alpha power);

Hypothesis 1b: SUVO compared to placebo will improve acute stress reactivity as measured by physiological responses (cold-pressor task induced cortisol and HR/BP) and subjective ratings (Visual Analog Scale; Depression Anxiety Stress Scale).

Hypothesis 1c: SUVO compared to placebo will reduce cue reactivity/craving as measured by LPP to methamphetamine images and self-report (Brief Substance Craving Scale).

Exploratory Aim 2: Evaluate the preliminary safety and side effects profile of SUVO.

**Primary outcome measures:** self-reported sleep, resting state alpha power, LPP, self-reported stress, and cortisol measured at each study visit after 1-week of SUVO, washout, and PL; total sleep time and wake after sleep onset measured nightly via actigraphy watch

**Secondary outcome measures:** methamphetamine use (TLFB and UDS) measured at each study visit after 1-week of SUVO, washout, and PL; side effects questionnaire, BDI, and CSSRS measured at each study visit after 1-week of SUVO, washout, and PL

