## Methods:

**Overall study design.** We will use a two-group cross-over design. Each group will complete three conditions, each lasting one week. 12 participants will be randomized to one of the two groups. Group one (n=6) will receive one-week placebo, one-week washout, and one-week SUVO. Group two (n=6) will receive one-week SUVO, one-week washout, and one-week placebo. During the washout period, the participants will not receive any pills. Eligibility criteria and baseline measures will be collected on Day 0 before the start of week one. Participants will come to the clinic once a week on Monday for 4 weeks. On Day 1 (Monday) of the first week, the participants will receive their medication and actigraphy watches. Each following Monday, they will complete self-report and drug use measures, as well as the laboratory tasks (cold pressor and EEG). Table 1 outlines the schedule of assessments. We will aim to enroll a total of 16 participants to complete 12, with dropouts being replaced, if possible.

**Participants, Recruitment, and Setting.** The participants will consist of non-treatment-seeking individuals meeting DSM-5 criteria for MA use disorder. All participants will be between the ages of 18-45 and fluent in English. IRB NUMBER: HSC-MS-22-0796 IRB APPROVAL DATE: 10/09/2023

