### Specific Hypothesis Testing.

**Aim 1:** GLMM for repeated measures will separately model each outcome measure as a function of treatment condition, with Level-2 effects included for best fit. Outcomes will include measures of sleep (H1a: actigraphy; self-report sleep quality; EEG), acute stress reactivity (H1b: physiological responses; subjective ratings) and cue reactivity/craving (H1c: LPP to methamphetamine images; self-report craving)

**Aim 2:** Descriptive statistics will evaluate the frequency of adverse events (AEs) and severe adverse events (SAEs) between and within conditions. Logistic regression will evaluate presence (vs. absence) of specific AEs as a function of condition.

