### Sample Size and Power.

The current study is primarily concerned with deriving a preliminary range of plausible effect sizes for the effect of treatment; as such, power estimates are provided here purely as due diligence. Frequentist estimates rely on G\*Power 3.1.9.7 and focus on a simplified model predicting the effect of treatment on one given normally-distributed outcome. Assuming two-sided alpha = 0.05, N = 12, 3 total measurements, a correlation among repeated measures of  $r = 0.15$ , the current proposal has 80% power to detect an effect size Cohen's  $f = 0.59$ . Notably, Bayesian inference will provide probabilistic estimates of the effect of treatment irrespective of sample size.

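### Choosing random effects by fit can drop the participant-by-week term for the nightly actigraphy outcomes and modestly inflate the SUVO-versus-placebo type I error

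*Combined protocol and SAP*

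**What the plan says.** The overview under Data Analytic Strategy sets the general rule: every model is to handle the repeated observations through the "best-fitting structure of level-2 intercepts/slopes". Specific Hypothesis Testing repeats it for Aim 1, where each outcome is modelled on treatment condition "with Level-2 effects included for best fit". Neither place names a selection criterion, a minimum random structure or a method for the denominator degrees of freedom.

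Primary Hypotheses and Specific Aims lists among the primary outcomes "total sleep time and wake after sleep onset measured nightly via actigraphy watch". Treatment, by contrast, is set by the week. Methods (overall study design) states: "Each group will complete three conditions, each lasting one week". The conditions are placebo, washout and SUVO, and the schedule of assessments shows actigraphy in all three weeks. On sample size, the overview says: "We will aim to collect full data on 12 participants". The actigraphy paragraph under Measures names the two quantities to be calculated. It does not say whether the value analysed is a night or a weekly mean.

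Under Multiplicity, a priori frequentist models are tested at two-sided 0.05, and false discovery rate control is reserved for post hoc analyses.

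**The concern.** Treatment is allocated to participant-weeks, so the SUVO-placebo difference must be judged against how much a participant's weekly level varies from week to week beyond nightly noise. In a mixed model that is the participant-by-week (participant-by-condition) variance. A model with a participant intercept only treats the seven nights in a week as independent given the participant. It therefore credits the treatment contrast with more information than the design provides.

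The stated rule lets the same 12 participants' data decide whether this term stays. Fit criteria have little power to detect a modest variance component in so small a sample. When they miss it, the standard error is too small and the degrees of freedom too many. The study's stated purpose is a preliminary range of plausible effect sizes. The fault would narrow that range as well as lower p-values, and a Bayesian model without the term would be overconfident in the same way.

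**Working it through.** **The plan's own figure.** The power statement reads "Assuming two-sided alpha = 0.05, N = 12, 3 total measurements, a correlation among repeated measures of" r = 0.15, with 80% power at f = 0.59. As a between-group repeated-measures test, λ = f²Nm/(1+(m−1)r) = 0.3481 × 12 × 3 / 1.30 = 9.64 on (1, 10) df, which gives 79.9%. The figure reproduces in that form. It rests on three measurements per participant, so it does not describe a model of nightly data.

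**Inputs from the documents.** n = 12 participants; K = 7 nights per week; J = 2 weeks (SUVO and placebo) or J = 3 (washout included); two-sided 0.05.

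**Assumptions.** r is the ratio of participant-by-week variance to night-to-night variance, taken from 0 to 0.5. Nights are independent within a week, variances are equal across weeks, and the data are complete.

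**Degrees of freedom.** Week level: (n−1)(J−1) = 11 or 22. Night level: nJ(K−1) = 144 or 216. With the term dropped the two are pooled: 155 or 238.

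**Standard errors, two weeks, night variance = 1.**
- True: √[2(r + 1/7)/12].
- Reported without the term: √[2p/(7 × 12)], with p = [11(1 + 7r) + 144]/155.
- At r = 0.2: true √(2 × 0.3429/12) = 0.239; p = 170.4/155 = 1.099; reported √(2 × 1.099/84) = 0.162. The true value is 1.48 times the reported one.

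**Type I error after selection.** Null trials were simulated from the ANOVA strata, 400,000 per setting, with a one-parameter participant-by-week term. The term was kept if the REML deviance fell by more than 2 (AIC), 3.84 (likelihood-ratio test at 0.05) or the log of the number of observations (BIC: ln 168 = 5.12 or ln 252 = 5.53). The contrast was then tested in the retained model with that model's df. Figures repeat to within about 0.2 points.

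| r | 2 weeks: AIC / LRT / BIC (%) | AIC drops term | 3 weeks: AIC / LRT / BIC (%) | AIC drops term |
|---|---|---|---|---|
| 0 | 4.7 / 4.9 / 5.0 | 94% | 4.7 / 4.9 / 4.9 | 93% |
| 0.05 | 7.0 / 8.0 / 8.2 | 78% | 6.6 / 7.5 / 8.0 | 68% |
| 0.1 | 7.9 / 9.6 / 10.4 | 59% | 6.7 / 8.1 / 9.2 | 40% |
| 0.15 | 7.9 / 10.0 / 11.1 | 43% | 6.1 / 7.5 / 8.8 | 21% |
| 0.2 | 7.5 / 9.7 / 11.1 | 30% | 5.7 / 6.7 / 7.8 | 10% |
| 0.3 | 6.5 / 8.3 / 9.7 | 15% | 5.2 / 5.6 / 6.2 | 3% |
| 0.5 | 5.5 / 6.3 / 7.1 | 4% | 5.0 / 5.1 / 5.2 | under 1% |

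With the week-level error always used, which is the same as testing weekly means, type I error is 5.0% in every row.

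**Sensitivity.** For two weeks, an unstructured intercept-plus-slope model (two extra parameters) was fitted directly by REML, 1,000 trials per ratio. It peaks at 8.2% (AIC), 9.9% (LRT) and 13.7% (BIC), with a Monte Carlo standard error of about 1 point.

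**The case against.** The strongest reply is that the plan lists slopes as well as intercepts as candidates. A condition slope is the participant-by-condition term, so the plan never commits to an intercept-only model. This stands, and it rules out a stronger reading that a reader might infer. If the term were always dropped, type I error with two weeks would be about 12% at r = 0.1 and 30% at r = 0.5. Those figures describe an analysis that the plan does not specify. Under selection, the term is missed mostly when it matters least.

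A reader might also infer that selection will usually miss the variance. That depends on a ratio the documents do not give: AIC drops the term in 78% of two-week trials at r = 0.05, but in 4% at r = 0.5.

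Three further points stand in part:
- Nightly values as the unit of analysis are an inference. The outcomes are measured nightly, but three measurements in the power statement would also fit one value per condition. If weekly means are used, the problem disappears.
- The 11 and 155 df hold only if washout is left out. With all three weeks modelled, the df are 22 and 238 and the inflation is smaller.
- The study is a 12-person proof of concept with parallel Bayesian models, so less hangs on a single p-value. This limits the consequence. It does not help the interval width, because the same omission narrows posteriors too.

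None of this removes the problem. The rule is stated twice, and nothing requires the term to be kept or the nights to be averaged.

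**Conclusion.** The concern holds in a limited form. For total sleep time and wake after sleep onset, the stated rule allows the error term that matches the unit of treatment to be removed on the strength of the same small data set. If nightly values are analysed, type I error after selection is about 5-8% (AIC), 5-10% (LRT) or 5-11% (BIC) with two weeks, and about 5-7%, 5-8% or 5-9% with three, against a nominal 5%. The inflation is greatest at ratios of roughly 0.1 to 0.2, absent at zero and small at 0.5.

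These sizes rest on the assumed ratio, independent nights and complete data. Serial correlation between nights would add to the week-level variation that an intercept-only model misses; it is not in these figures. The point does not extend to outcomes taken once per visit, where there is one value per participant per condition and nothing to pool. It is a modest excess on two primary outcomes. It is worth correcting because the plan states the rule outright and the correction is cheap.

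**What to change.** For the two nightly outcomes, replace selection by fit with a structure fixed before the data are seen. The preferred form is one mean per participant per week, analysed with a participant effect and t-based small-sample degrees of freedom. The alternative, equivalent in balanced data when the estimated variance is above zero, is a participant intercept plus a participant-by-week random effect that is always kept. State which weeks enter the model, and use the same structure in the Bayesian model.

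This changes SAP wording only; no data or visits are added. If the extra variance is truly zero, the critical value is about 11% larger with two weeks (2.201/1.975, 11 versus 155 df) or 5% larger with three (2.074/1.970, 22 versus 238 df). The variance-component form can be more conservative because its estimate cannot go below zero. With two weeks, zero true variance and 11 df, the estimate sits at zero in 55% of simulated trials and type I error falls to 2.2%. That is one reason to prefer weekly means.

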**Cue Reactivity/Craving (LPP).** The late positive potential (LPP) is an event-related potential component thought to reflect the motivational relevance of visual stimuli. The LPP to drug images is enhanced in drug users compared to controls, is correlated with craving, and tracks with abstinence, thus serving as an objective measure of cue reactivity/cue-induced craving. EEG will be collected on test days prior to the cold pressor task. The Picture Viewing Task will be used to elicit the LPP. Suvorexant might lead to decrease drug use through reducing reactivity toward drug cues. Therefore, the picture viewing task will provide this neural assessment of cue reactivity. In the task, the participants view images in four categories, pleasant, unpleasant, methamphetamine, and neutral. The other image categories are necessary, so that we can ensure the brain reactivity is specifically in response to drug images and not just salient images. This is a standard task used in the EEG literature and a meta-analysis shows drug users have an increased

response to drug images with a large effect size.

**Cue Reactivity/Craving (Self-Report).** The Brief Substance Craving Scale (BSCS) will be used to assess current MA craving. The BSCS will be assessed on each test day prior to laboratory tasks.

**Safety/Side Effects.** A 31-item questionnaire will be administered on each test day to assess side effects and adverse events. The Colombia Suicide Severity Rating Scale (CSSRS) and Beck's Depression Inventory (BDI) will be administered at each visit per NIH guidelines. Breath alcohol concentration will also be assessed at each visit to assess for current intoxication.

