In addition to the rigorous screening criteria for inclusion. At the end of each experimental day, cardiovascular measures will be taken and the subject will be evaluated for signs of impairment or side effects, by a research assistant and then by the research nurse, medical director, or PI. The assessment battery includes subjective effects questionnaire, nystagmus, touching nose, balance, and walking a straight line). If cardiovascular measures are normal, within the range of pre-dose levels, and the subject is determined to be unimpaired, the subject will be released. If any signs of intoxication are detected, participants will be required to remain at the experimental site until such symptoms are no longer observed.

In the event of either an unexpected adverse event or a prolonged period of intoxication, we have several measures in place. First, [name] (CNRA medical director) has clinical experience and training in emergency medicine. Thus, a physician will be in the immediate vicinity of laboratory at all times. Offices and clinical space are within 100 feet of the lab. Collaborating MDs can be paged at any time during the day. Second, Ben Taub Hospital, a level 5 emergency medical center is located just minutes away from BBSB. Finally, in the event of extended sedation, intoxication, or impairment, in which any subject does not appear clear-headed, feeling well, and in full control of his or her behavior, two steps will be taken. First, the subject will remain in the lab until such time that the primary or a co-investigator deems that it is safe for him or her to leave (e.g., passing the sobriety test described above). In the event of extended impairment, we will arrange (and pay for) a taxi service to drive the subject back to his/her home rather than having to use METRO. We will administer the Columbia Suicide Severity Rating Scale (CSSRS screening version) at each visit to assess suicidality and depressive symptoms, consistent with current FDA best practices. If the screening indicates change in suicidal ideation, we will administer the full version. If suicidality is judged to clinically significant as per CSSRS scoring criteria, we will (1) report the event to CPHS within 48 hours; (2) remove the patient from the study; (3) make a referral to either the BBSB outpatient mood disorders clinic or UT HCPC, depending on consultation from Dept of Psychiatry outpatient faculty at BBSB.

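### Dropouts are excluded according to an unstated amount of data, and the safety analysis has no named population

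*Combined protocol and SAP*

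**What the plan says.** The Overview of the Data Analytic Strategy aims for full data on 12 participants and then states: "Other participants who drop out or are withdrawn will be excluded from analyses, depending on how much data we are able to collect". Two further routes follow. For small gaps: "If only a few data points are missing, generalized linear mixed modeling will natively handle missing outcome data". For the rest: "any other issues related to missing data will be handled via explicit modeling of missingness or imputation". None of the three routes has a boundary.

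The same Overview opens with its scope: "Analyses will primarily rely on generalized linear modeling (GLM) for cross-sectional analyses and generalized linear mixed modeling (GLMM) for longitudinal analyses".

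Under Specific Hypothesis Testing, Aim 2 reads "Descriptive statistics will evaluate the frequency of adverse events (AEs) and severe adverse events (SAEs) between and within conditions" and "Logistic regression will evaluate presence (vs. absence) of specific AEs as a function of condition". It does not say who is included or which record supplies the events. In the Measures section, Safety/Side Effects says "A 31-item questionnaire will be administered on each test day to assess side effects and adverse events". The schedule table puts the first test day on the Monday after week 1.

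Overall study design plans 16 enrolled to reach 12 completers, with replacement of dropouts where possible. The protection-against-risks text provides for removal after clinically significant suicidality ("report the event to CPHS within 48 hours; (2) remove the patient from the study") and, more generally, after an abnormal event if indicated.

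**The concern.** The plan expects partial records but leaves open how much data keeps a person in. A mixed model handles missing values only for people left in the data set, and this rule can take them out first. Whoever applies it can do so with the outcomes in view.

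Two things are at stake. For Aim 1, the purpose stated under Sample Size and Power is a range of plausible effect sizes, and the Project Summary says the work is to support a later grant. That range may describe completers only, or a group chosen afterwards. For Aim 2, withdrawal can itself be the safety outcome. The word for what people are excluded from is unqualified, and logistic regression is one of the model types the Overview covers. The rule can therefore be read to drop someone withdrawn for an event on suvorexant from the reported comparison between conditions.

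**Working it through.** **Inputs.** Enrolled 16, completers 12 (Overall study design). Three laboratory visits and about 21 actigraphy nights (schedule table). Correlation r = 0.15 (Sample Size and Power); r = 0.5 is added as an assumption to show the range. The documents give no dropout reasons or timing, so the cases below are assumed. Outcomes are in SD units under no true effect, with a random intercept and condition (suvorexant, washout, placebo) as in Aim 1. The plan attaches no number to the rule, so there is no figure of its own to reproduce. The share that could be affected is (16 − 12)/16 = 25%, or less if some are never randomised or dosed.

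**What each person has.**
- Completer: 3 laboratory visits, about 21 nights.
- Leaves after period 1: 1 of 3 visits, about 7 of 21 nights. The mixed model can use these; the rule can discard them.
- Withdrawn during week 1: no laboratory visit and no side-effects questionnaire, so adverse events are in the Adverse Event Log only.

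**1. Dropout unrelated to outcome: precision lost.** Variance components are treated as known, with 12 completers plus 4 partial records, 2 per sequence.
- Completers only: SE² = 2(1 − r)/12, so SE = 0.376 (r = 0.15) and 0.289 (r = 0.5).
- Adding 4 people with one visit: SE² = 2 / [12/(1 − r) + 2]. For r = 0.15, 2/(14.118 + 2) = 0.1241, SE = 0.352. For r = 0.5, 2/(24 + 2) = 0.0769, SE = 0.277.
- Adding 4 people with two visits: SE² = 2 / [12/(1 − r) + 2/(1 − r²)]. For r = 0.15, 2/(14.118 + 2.046) = 0.1237, SE = 0.352. For r = 0.5, 2/(24 + 2.667) = 0.0750, SE = 0.274.
- Completer equivalents, 12 × (SE ratio)²: 13.7 and 13.7 (r = 0.15), 13.0 and 13.3 (r = 0.5). Discarding the four loses 1.0 to 1.7 completers. There is no bias.

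**2. Same dropout, threshold left open.** 40,000 simulated trials of 16 people (8 per sequence), 4 leaving at random, REML variances. Each single threshold (at least 1, at least 2, or all 3 visits) rejects at 4.9–5.1%. Taking the smallest p-value of the three gives:

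| Who leaves | r = 0.15 | r = 0.5 |
|---|---|---|
| 2 after visit 1, 2 after visit 2 | 7.3% | 6.8% |
| all 4 after visit 1 | 6.7% | 6.1% |

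The Monte Carlo SE is 0.13 points. A check with variances treated as known gave 6.2–7.1%. The all-observed and completer estimates differ by a median of 0.05–0.09 SD (90th percentile 0.14–0.22).

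**3. Worst case.** The k = 1 to 4 suvorexant-first participants with the worst suvorexant values leave after period 1. E denotes the expected mean of the retained best normal values.
- 8 randomised per sequence: shift = (8 − k)/(16 − k) × (1 − r) × E(best 8 − k of 8). At k = 4, r = 0.15: 4/12 × 0.85 × 0.727 = 0.206. Range 0.08–0.21 SD (r = 0.15) and 0.05–0.12 SD (r = 0.5).
- 6 completers per sequence, dropouts replaced in the same sequence: shift = 0.5 × (1 − r) × E(best 6 of 6 + k). At k = 4, r = 0.15: 0.5 × 0.85 × 0.595 = 0.253. Range 0.10–0.25 SD and 0.06–0.15 SD.

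Divided by 0.376 or 0.289, these are about 0.2 to 0.7 SE. The all-observed mixed model, 20,000 simulations with known variances, shifts by −0.005 to 0.002.

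**4. Safety.** Suppose one person is withdrawn for an event on suvorexant and no completer has it. Completers only: 0/12, exact 95% upper limit 1 − 0.025^(1/12) = 26.5%. All dosed: 1/13 = 7.7% (0.2% to 36.0%).

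**The case against.** The strongest reply is about scope. The sentence sits among remarks on missing outcome data and may be meant for Aim 1 only. Aim 2 is led by descriptive statistics, and nothing there removes anyone. Events in withdrawn people still enter the Adverse Event Log and reach the monitoring committee and the IRB. All of this is true, so the safety part is an ambiguity in the reported summary and not a failure of surveillance.

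Second, the plan does not prescribe completers only. Its wording lets partial records stay, and cases 1, 3 and 4 measure the extreme. That stands too, but the discretion is itself the problem.

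Third, the effects are modest. Case 1 enlarges the SE by roughly 4–7%, case 2 needs someone to pick the smallest p-value, case 3 is extreme by design, and the intervals in case 4 overlap widely. Some of the 16 may also fail screening, since consent comes before eligibility assessment. These points limit the weight, not the finding.

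Fourth, the near-zero shift for the all-observed model holds because dropout there depends only on an observed value. Someone withdrawn during week 1 has no laboratory visit and still drops out of those outcomes under any rule. Also, removal after the suicidality scale follows a visit, so only the general abnormal-event clause supports removal between visits. Both are fair limits.

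**Conclusion.** The concern holds. Confidence is high that no threshold separates exclusion, the mixed model and imputation, and moderate that the rule reaches Aim 2. It should be fixed, but it does not undermine the study, which is preliminary and whose safety aim is exploratory.

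Under ordinary dropout the cost is 1.0–1.7 completer equivalents out of about 13–14 and no bias. Leaving the threshold open can raise the false-positive rate per outcome by about 1 to 2 points, and the plan's FDR control covers only post hoc analyses. The 0.05–0.25 SD shift toward benefit applies only in the assumed worst case. For safety, nothing changes if nobody is withdrawn for a suvorexant event, and the Medication section reports no serious adverse effects in the group's earlier cocaine study. If one is, the issue is an event missing from the report, not a precise rate. The figures assume up to four dropouts, r of 0.15 or 0.5, and a random-intercept model.

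**What to change.** Replace the exclusion sentence with text to this effect:

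> No one is excluded for the amount of data missing. Aim 1 mixed models include every randomised participant with at least one value of that outcome recorded after starting study medication (washout values included), up to withdrawal. Completers are a sensitivity analysis. Any missingness model or imputation is named before outcome data are seen and reported as a sensitivity analysis. Aim 2 includes everyone who took at least one dose. Events come from the Adverse Event Log as well as the questionnaire and are counted under the condition at onset. Washout-onset events are shown separately with the preceding condition. The denominator for each condition is those dosed in it. Withdrawals are reported by condition and reason.

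Replacement to reach 12 completers can stay, and no clinical rule changes. The essential parts are the Aim 1 inclusion rule and the Aim 2 population and source; the display details are secondary.

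The cost is SAP wording, slightly more analysis work and unbalanced data. It needs no extra participants or visits, because the log is already planned. The change does not supply a questionnaire for someone withdrawn between visits, and it does not remove bias from dropout that depends on unobserved response.

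### The Aim 1 covariate screen has no pre-dose limit and names no primary model; in this crossover, what it can select is mainly what SUVO may have changed

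*Combined protocol and SAP*

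**What the plan says.** Under Data Analytic Strategy, Overview (Confounders), the plan begins with a look at the data: "Preliminary data analyses will inspect relationships between sample characteristics, predictors, and outcomes via GLMM". It then gives the selection rule, "Variables that demonstrate a relationship with both the predictor and outcome in a model meet criteria for being potential confounders", and the reporting rule, "We report the simpler model if inferences are not affected by these covariates and report both models otherwise". It gives no covariate list, no limit on when a covariate may be measured, no threshold for a relationship and no exclusion of mediators. It does not say which model carries the conclusion when both are shown.

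For Aim 1 the predictor is treatment condition (Specific Hypothesis Testing): "GLMM for repeated measures will separately model each outcome measure as a function of treatment condition". The design is stated under Methods, Overall study design: "We will use a two-group cross-over design. Each group will complete three conditions, each lasting one week". Allocation is to sequence ("12 participants will be randomized to one of the two groups"), and washout always falls in week 2, for example "Group one (n=6) will receive one-week placebo, one-week washout, and one-week SUVO". Equal completed sequences are intended but not assured: "We will aim to enroll a total of 16 participants to complete 12, with dropouts being replaced, if possible".

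**The concern.** A screen on association with predictor and outcome is meant for settings where exposure was not assigned by design. Here order is randomised and each person supplies both conditions. Age, sex or severity of use cannot differ between a person's SUVO week and the same person's placebo week. For a variable to be related to condition it must change within person, and the repeated measures in Table 1 are taken at the end of each week, so in the treatment weeks they follow dosing. A relationship with condition then mostly means that SUVO changed the variable.

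The protocol describes such pathways itself. The section on cue reactivity and the LPP expects SUVO to lower drug use by lowering reactivity to drug cues. The Background links poor sleep to craving and stress. Adjusting for a variable on such a path estimates the part of the effect that bypasses it, which is not the total SUVO effect that Hypotheses 1a to 1c concern. The adjusted model also appears exactly when it changes the inference, so the data decide whether the reader gets one answer or two.

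**Working it through.** **Inputs from the documents.** N = 12, 6 per sequence (Overall study design). Two-sided alpha 0.05, three measurements, correlation among repeated measures r = 0.15 (Sample Size and Power).

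**Assumptions.** A relationship means p < 0.05, because the plan gives no threshold. The documents give no mediator strengths, so a range is used. Effects are in within-condition SD units, with benefit positive.

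**The plan's own figure.** The plan states 80% power at f = 0.59. The between-groups repeated-measures form gives λ = 0.59² × 12 × 3 / (1 + 2 × 0.15) = 9.64 on 1 and 10 df, power 0.799, so the figure reproduces. (The within-subject form with three measurements gives about 0.90; that is a separate matter.) This point does not rest on that figure; it uses only N and r. The SD of a paired difference is √(2 × (1 − 0.15)) = 1.30, the unadjusted SE is 1.30/√12 = 0.38, and power for a true 1.0 SD effect is 0.68.

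**Step 1: fixed characteristics.** Code condition ±½. Each person contributes x(+½) + x(−½) = 0, so the covariance with condition is exactly 0 in complete data. With 1 to 3 of the 24 SUVO and placebo cells missing, the mean absolute correlation is 0.04 to 0.07, and no such variable passed the predictor link in 5,000 runs.

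**Step 2: time-varying variables that SUVO does not affect.** These pass both links in 0.2% to 2.9% of trials (slope on outcome 0 to 0.7).

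**Step 3: post-dose mediators.** Let SUVO move the mediator by a, and the mediator move the outcome by b per unit. With dY and dM the paired differences, the adjusted estimate is mean(dY) − b̂ × mean(dM), with expectation total − a × b. The screen was applied in every simulated trial.

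| a | b | True total | Selected | Adjusted mean, all trials | Adjusted mean, selected trials | Models disagree on significance, selected trials |
|---|---|---|---|---|---|---|
| 0.5 | 0.5 | 1.0 | 8% | 0.75 | 0.48 | 65% |
| 1.0 | 0.3 | 1.0 | 10% | 0.70 | 0.23 | 60% |
| 1.0 | 0.5 | 1.0 | 25% | 0.51 | 0.21 | 65% |
| 1.0 | 0.7 | 1.0 | 51% | 0.30 | 0.20 | 72% |
| 1.0 | 0.225 | 0.9 | 7% | 0.68 | 0.15 | 50% |
| 1.0 | 0.45 | 0.9 | 17% | 0.45 | 0.04 | 52% |

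The last two rows place 25% and 50% of a 0.9 SD effect on the pathway and let the mediator add to the outcome variance; the others hold outcome variance fixed. The all-trials column follows from the assumptions (for example 0.9 × 0.75 = 0.675). The selected-trials column shows what the rule adds: it picks trials in which b̂ and mean(dM) both ran high, so their product overshoots a × b.

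**Step 4: period.** The correlation of period with condition is (n₁ − n₂)/12: 0 at 6:6, 2/12 = 0.17 at 7:5 (p = 0.44 on 24 observations) and 4/12 = 0.33 at 8:4 (p = 0.11). Neither imbalance passes a 0.05 screen. If the later week shifts the paired difference by an assumed 1 SD, leaving period out biases the contrast by 0.17 SD at 7:5 and 0.33 SD at 8:4.

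**The case against.** The strongest reply has three parts, and much of it stands.

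First, the text speaks of sample characteristics and names no post-dose covariate. Methamphetamine use and side effects are listed as secondary outcomes. If only baseline characteristics were ever screened, the rule would admit almost nothing and do no harm. That reading is possible, but the selection sentence says variables without limit. On the harmless reading the rule has no function for this contrast.

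Second, the unadjusted model is reported under either branch, alone or beside the adjusted one. A reader might infer that the rule strips part of the SUVO effect out of the report; it does not. What remains is that the plan does not rank the two results.

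Third, this is a pilot that says its main purpose is a plausible range of effect sizes, and a mediator is often not selected: with 25% or 50% of a 0.9 SD effect on the pathway, it is chosen in only 7% or 17% of trials. That limits how often harm occurs. It does not make the adjusted estimate a valid member of the range when the rule does fire.

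A reader might also infer that the screen cannot find any real confounder. That is too absolute. Dropout and replacement can leave unequal sequences, and a large enough imbalance could be flagged. Nor are period and sequence the only design threats: carryover is another, and sequence, a fixed property of the person, does not stand on the same footing as period.

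**Conclusion.** The point holds as a defect in a stated rule. For the SUVO versus placebo contrast the screen almost never identifies a true confounder. What it can select is mainly variables measured after dosing, and it would usually miss a 7:5 or 8:4 period imbalance. That post-dose variables are the main candidates is inferred from the design and assessment schedule; the plan does not say it.

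The harm is conditional. Across the assumed strengths a mediator is selected in about 7% to 50% of trials. When it is, the adjusted estimate averages about 0.0 to 0.2 SD if SUVO moves the mediator by 1 SD, and 0.48 SD in the case examined with a 0.5 SD shift, against a true 0.9 to 1.0 SD. The two models then give different significance calls in about half to three quarters of trials, with no rule for which one counts. These figures rest on a 0.05 screening threshold, r = 0.15 and assumed mediator strengths. The zero correlation of fixed characteristics with condition needs only complete data.

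**What to change.** For the Aim 1 SUVO versus placebo contrast:

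- Drop the association-based screening.
- Name one primary model: treatment condition and period, with sequence as a design term. Code period as week 1 versus week 3. Washout is always week 2, so a three-level week factor would be aliased with the washout level if all three conditions are modelled.
- State that no variable measured after the first dose enters the primary model.
- Label any model adjusting for methamphetamine use, adherence or side effects as exploratory, and say that it does not estimate the total effect.

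These terms do not remove carryover, which needs its own statement.

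The cost is SAP wording and about one residual degree of freedom for period; sequence is a between-person term. At 6:6 with no period effect, power for a 1.0 SD effect goes from 0.68 to 0.67. With an assumed 1 SD period shift in the paired difference, fitting period raises it from 0.47 to 0.67. At 8:4 the SE becomes ½ × 1.30 × √(1/8 + 1/4) = 0.40 instead of 0.38, in exchange for removing the 0.33 SD bias shown above.
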